6.5. Duration of Therapy

It is intended that subjects will be treated until radiologically determined progressive disease per RECIST v1.1 or unacceptable study drug-related toxicity. However, a subject may discontinue study treatment at any other time. Reasons for discontinuing study treatment include, but are not limited to the following:

- Documented disease progression (radiographically) per RECIST.
- Clinical deterioration sufficient to prevent further radiological assessment.
- Extraordinary medical circumstances: If at any time the constraints of this protocol are detrimental to the patient's health, study treatment should be discontinued.
- Pregnancy.
- A study drug related adverse event, prior to disease progression, which in the opinion of the Investigator precludes further treatment with all study drugs.
- Subject requests to stop further treatment or withdraws consent for the study.
- Development of an intercurrent medical condition or need for concomitant therapy that precludes further treatment with all study drugs.

Discontinuing study treatment is not the same as withdrawing consent to be in the study.

Subjects discontinuing study treatment must continue with all ongoing protocol requirements, as detailed in [Section 8](#), unless they have withdrawn consent for further follow-up.

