6.6. Treatment Delays and Termination due to Toxicity (Irinotecan + Dinutuximab)

For subjects randomized to Group B, irinotecan and dinutuximab are intended to be given on the same day of each cycle (Day 1 \pm 2 days). A cycle for the combination may be delayed up to 7 days due to unresolved toxicity of one drug or the other. In this case, the cycle for irinotecan and dinutuximab would be shifted by up to 7 days. If there is unresolved toxicity for irinotecan resulting in a treatment delay of >7 days, subjects should continue with dinutuximab alone for that cycle and irinotecan should be omitted until the next cycle. Conversely, if there is unresolved toxicity for dinutuximab resulting in a treatment delay of >7 days, subjects should

continue with irinotecan alone for that cycle and dinutuximab should be omitted until the next cycle. Treatment delays of >7 days should be discussed with the Medical Monitor.

Subjects should continue with dinutuximab alone on schedule if irinotecan is terminated for toxicity. If dinutuximab is terminated for toxicity, irinotecan should continue on schedule. In some cases, coincident toxicities may occur resulting in delay or termination of both dinutuximab and irinotecan.

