- Group B: Dinutuximab + Irinotecan; or
- Group C: Topotecan.

Subjects randomized to Group A or Group B will receive irinotecan at a dose of 350 mg/m² on Day 1 of each cycle.

Subjects randomized to Group B will also receive dinutuximab on Day 1 of each cycle beginning with a starting dose of 16 mg/m² IV. Dose escalation and de-escalation for dinutuximab will occur as in Part 1. The maximum dose of dinutuximab that may be administered is 17.5 mg/m². If this dose is reached, the last dose increment would be 1.5 mg/m².

Subjects randomized to Group C will receive topotecan 1.5 mg/m² IV for the first 5 consecutive days of each 21-day cycle.

There is a 2-day window around administration of study drugs on Day 1 of each cycle except for the first cycle (initial treatment should begin within 3 working days of enrollment or randomization). All subjects (Part 1 and Part 2) will be treated until disease progression or intolerance. All subjects will be followed for disease progression even those discontinuing study drug for other reasons (e.g., intolerance).

An end of treatment (EOT) visit will occur approximately 30 days after the last administration of all study drugs (dinutuximab and/or chemotherapy) or prior to the initiation of subsequent treatment (whichever occurs first).

For subjects receiving dinutuximab, immunogenicity follow-up will continue for up to 16 weeks following the last dose of dinutuximab to assess anti-drug antibodies (ADA) and neutralizing antibodies (NAb).

Follow-up for survival will continue until the subject has withdrawn consent, is lost to follow-up, has died, or until the Sponsor makes a decision to close the study. It is important that all subjects are followed for survival. No crossover is allowed given OS is the primary endpoint.

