4.8 Study Drug Exposure

4.8.1 Exposure

A frequency table will display the number (%) of patients in each treatment group according to the total number of cycles initiated, as of the cut-off date for analysis. Duration of treatment for each subject will be calculated as the number of days from the date of the first dose of study medication to the date of the last dose taken, inclusive. Duration of treatment, total number of doses administered, cumulative dose, dose intensity, and relative dose intensity will be summarized for each treatment group and each treatment using descriptive statistics (n, mean, median, SD, inter-quartiles, minimum, and maximum) based on the Safety Analysis Set.

For Part 2 subjects, methods for calculating cumulative actual dose, cumulative planned dose, dose intensity, and relative dose intensity for each medication are as follows:

- Cumulative actual dose (mg/m²): Sum of {Starting dose level for each cycle};
- Cumulative planned dose (mg/m²): Sum of {Planned dose level for each cycle}, i.e.;
 - Dinutuximab – (Number of cycles that should have been initiated between the first dose date and the last dose date – 1) x 17.5 + 16, if number of cycles ≥ 2; otherwise, 16 mg/m² if number of cycles = 1;
 - Irinotecan – (Number of cycles that should have been initiated between the first dose date and the last dose date) x 350;
 - Topotecan – (Number of cycles that should have been initiated between the first dose date and the last dose date) x 1.5 x 5;
- Dose intensity (mg/m²/day): Cumulative actual dose / (Last dose date – first dose date + 21);

- Relative dose intensity (%): $\text{Dose intensity} / \{ \text{Cumulative planned dose} / [(\text{Number of cycles that should have been initiated between the first dose date and the last dose date}) \times 21] \} \times 100$.

For each treatment administered, infusion start and stop times, the volume infused, and reasons for any dose reductions or interruptions will be listed for each subject. The number of subjects requiring a dose modification (reduction, delay or interruption) will be summarized descriptively by treatment group.

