4.10 Safety Analysis

4.10.1 Adverse Events – Part 1

Toxicities reported during Part 1 (intrasubject dose escalation) will be listed for individual subjects by dinutuximab dose at time of onset. Pain severity scores will also be listed by dinutuximab dose, cycle, and time since start of infusion.

4.10.2 Adverse Events – Part 2

AEs will be coded using MedDRA Version 20.0 or higher. Treatment-emergent AEs (TEAEs) will be grouped and tabulated by the MedDRA System Organ Class (SOC) and Preferred Term (PT). An AE that starts or increases in severity after the first dose of study medication and up

until 30 days after the last dose will be considered a TEAE. Severity of the AEs will be graded according to the NCI CTCAE Version 4.03.

All safety summaries will be generated for the Safety Analysis Set.

A safety overview table will present the number (%) of subjects in each treatment group with events in the following categories:

- Any TEAEs
- Treatment-Related TEAEs
- Grade ≥ 3 TEAEs
- Grade ≥ 3 Treatment-Related TEAEs
- Treatment-Emergent Serious Adverse Events (SAEs)
- Treatment-Related SAEs
- Grade ≥ 3 SAEs
- Grade ≥ 3 Treatment-Related SAEs
- TEAEs leading to Discontinuation of Study Treatment
- TEAEs leading to Reduction in Dose of Study Treatment
- Fatal TEAEs
- Fatal Treatment-Related TEAEs

For these events, the difference between incidence rates for Group B (dinutuximab + irinotecan) minus Group A (irinotecan) will be presented, together with its 2-sided 95% confidence interval calculated using the Wilson score method. A lower bound $>$ zero may indicate excess risk in the dinutuximab group. The Wilson score method will be used to calculate 95% confidence intervals to ensure actual coverage closest to the nominal level.

The number and percentage of subjects experiencing TEAEs will also be summarized by SOC and PT. The following tables will be generated:

- Overall TEAEs
- Dinutuximab-Related TEAEs
- Irinotecan/Topotecan-Related TEAEs
- Grade ≥ 3 TEAEs,
- Dinutuximab-Related Grade ≥ 3 TEAEs
- Irinotecan/Topotecan-Related Grade ≥ 3 TEAEs
- TEAEs leading to discontinuation of Dinutuximab

- TEAEs leading to discontinuation of Irinotecan/Topotecan
- TEAEs leading to dose reduction of Dinutuximab
- TEAEs leading to dose reduction of Irinotecan/Topotecan
- Treatment-emergent SAEs
- Treatment-emergent SAEs related to Dinutuximab
- Treatment-emergent SAEs related to Irinotecan/Topotecan
- TEAEs with an outcome of death
- TEAEs by Maximum Grade

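### The SAP's excess-risk flag uses crude TEAE incidence under open-ended treatment, so unequal treatment time between Groups A and B can distort it in either direction

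*SAP*

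**What the plan says.** SAP 4.10.2 describes a safety overview table that "will present the number (%) of subjects in each treatment group with events in the following categories", and lists twelve categories. For each it gives the Group B minus Group A difference in incidence, "together with its 2-sided 95% confidence interval calculated using the Wilson score method". A lower bound above zero "may indicate excess risk in the dinutuximab group".

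The counting window is open at its far end. An event that starts or worsens after the first dose and "until 30 days after the last dose will be considered a TEAE". Treatment length is not fixed either. SAP 3 states: "All subjects (Part 1 and Part 2) will be treated until disease progression or intolerance". Protocol 6.5 agrees: "It is intended that subjects will be treated until radiologically determined progressive disease per RECIST v1.1 or unacceptable study drug-related toxicity". Group B has a further route to unequal exposure in Protocol 6.6: "Subjects should continue with dinutuximab alone on schedule if irinotecan is terminated for toxicity". The reverse also applies there, so either drug can carry on without the other.

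Exposure is measured. SAP 4.8.1 says: "Duration of treatment for each subject will be calculated as the number of days from the date of the first dose" to the last, inclusive. It is only summarised, however. Neither document, including the SAP table list, plans an exposure-adjusted event rate, a time-to-first-event analysis or a fixed-window comparison of adverse events.

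**The concern.** A percentage of subjects with at least one event compares risk cleanly when both arms are observed for similar times. Here time at risk depends on progression and tolerability, which are the things treatment may change. If dinutuximab delays progression, Group B subjects spend longer in the counting window and more of them record an event, even at the same monthly event rate. If Group B stops sooner for toxicity, its window shortens and a truly higher rate can look ordinary.

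Comparing the safety of Group B with Group A is a stated secondary objective, and the overview table is the only adverse event display for which the SAP plans a between-group interval and an interpretive sentence. Protocol 10.11 and SAP 5 give the DMC the same kind of crude comparison.

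**Working it through.** **The plan's own figure.** The documents state no operating characteristic for the flag. The nearest design figure is 306 deaths for about 80% power at an OS hazard ratio of 0.725, two-sided alpha 0.05. By the Schoenfeld formula, √306/2 × |ln 0.725| − 1.96 = 2.81 − 1.96 = 0.85, which is 80.3% power. The figure reproduces.

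**Inputs from the documents.** 184 subjects in each of Groups A and B; a two-sided 95% interval, so about 2.5% in the harm tail; a 30-day post-dose window, w = 30/30.42 = 0.986 months.

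**Assumptions not in the documents.** Group A median treatment time 2-4 months; exponential treatment time; constant monthly event hazard λ, equal in both arms; Group A incidence 10-70%; hazard ratio for stopping treatment (B vs A) of 1 down to 0.5, with 0.725 borrowed from OS as the reference. The Newcombe form of the Wilson score limit was used for the difference.

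**Formula.** With stopping hazard θ, incidence is p = 1 − exp(−λw) × θ/(θ + λ).

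**Worked case.** Group A median 3 months gives θ = ln 2/3 = 0.231. Incidence of 50% in A needs λ = 0.1626: exp(−0.1626 × 0.986) = 0.852, 0.231/0.3936 = 0.587, and 1 − 0.852 × 0.587 = 0.50. In B, θ = 0.231 × 0.725 = 0.1675, so p = 1 − 0.852 × 0.1675/0.3301 = 0.568. The artefact is 6.8 points. With 92/184 events in A, the lower limit first exceeds zero at 111/184 in B, a difference of 10.3 points. The exact binomial probability of a flag is 26%.

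**Range** (equal monthly event rates, all medians and incidences above):

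| Treatment-duration HR, B vs A | Chance of a false flag |
|---|---|
| 1 | 2.4-2.7% |
| 0.85 | 5-11% |
| 0.725 | 11-28% |
| 0.6 | 23-59% |
| 0.5 | 42-84% |

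**The other direction.** Take a true 1.5-fold event rate in B, with Group A median 3 months and incidence 50%. At equal treatment time, B's incidence is 61.8% and the flag fires in 63% of trials. If B stops sooner (duration HR 1.38), B's incidence is 55.5% and the flag fires in 19%.

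**Early events.** If first events are confined to cycle 1, with duration HR 0.725 and equal true incidence of 30% or 50%, the crude flag fires in about 2.5-3% of simulated trials, close to nominal.

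**Candidate remedies** (simulated, 184 per arm, Group A median 3 months, duration HR 0.725):

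- Constant hazard, equal rates: the person-month rate and a Cox time-to-first-event comparison each signal harm in about 2-3% of trials, against 22-26% for the crude rule at incidences of 30-70% (Cox run at 30% and 50% only).
- Cycle 1 events, equal incidence: the person-month rate difference falsely shows dinutuximab as safer in 30-45% of trials. The Cox comparison stays at about 2.5% on each side.
- Cycle 1 events, true 30% vs 40%: the crude rule detects the excess in about 53% of trials, the Cox comparison in about 52%, and the person-month rate in only 23-24%.

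**DMC looks.** With follow-up capped at an assumed 2, 3, 5.5 and 8 months for about 30, 50, 90 and 140 per group, duration HR 0.725 and the constant hazard of the worked case, the flag fires in 2.3%, 2.9%, 3.9% and 6.0% of trials.

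**The case against.** The strongest reply is that SAP 4.10.2 contains no decision rule. The wording is soft, the twelve categories overlap, Protocol 10.10 calls the safety summaries descriptive, and no alpha or consequence attaches to the table. The percentage of subjects with an event under treat-to-progression is also a legitimate quantity, because patients treated longer do experience those events. Duration, cycles and dose intensity are tabulated by arm, and listings give onset day, so an exposure imbalance would be visible. All of this stands and limits the weight of the point. It does not remove it: the SAP attaches a reading to the crude bound and does not say that exposure should be considered with it.

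A second reply is that a constant hazard fits the main toxicity poorly. In Part 1 (Protocol 1.15) the median duration of pain was under a day, with most cases resolving within hours of the infusion. That also stands. Where first events come early, the crude flag is close to nominal.

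A reader might infer more than this: that the flag will signal harm whenever dinutuximab works. The documents do not support that. The ratio 0.725 is an OS effect, while dosing stops at progression or intolerance. Even at that ratio the flag stays silent in most trials. A model that leaves out the 30-day tail gives 31% and 34% at Group A incidences of 30% and 50%. The tail has the same length in both arms and dilutes the difference, which brings these to 21-25% and 24-28%.

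A reader might also infer that the excess-risk statement should move to events per person-month. With early events that measure can hide real harm, as the simulations show.

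**Conclusion.** The point holds as a limited one. The flag rests on crude incidence, the treatment and counting windows are open-ended, and no time-adjusted comparison is planned. Under a constant, equal monthly event rate and a duration hazard ratio of 0.725, the chance of a false flag is 11-28% instead of about 2.5%. A false flag becomes more likely than not only at a duration hazard ratio of roughly 0.6 or below. With early-clustered events there is little distortion. Earlier stopping in Group B can hide real excess risk (63% down to 19% detection in the example), which is arguably the more important half. The effect at the DMC looks is small under the assumed follow-up, so this mainly concerns the final table. Every size given rests on treatment durations, hazard shapes and event rates that the documents do not supply.

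**What to change.** In SAP 4.10.2, keep the crude incidence table and its Wilson interval. For the same twelve categories, add a Group B vs Group A time-to-first-event comparison: Cox hazard ratio with 95% CI, censored at 30 days after the last dose (or at death or the analysis cut-off, if earlier). Show exposure-adjusted incidence rates as a supplementary display only. Add a sentence that a crude lower bound above zero is to be read together with the time-to-first-event result and treatment duration by arm. Do not replace the crude measure with the person-month rate.

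The cost is a few lines of SAP text and modest programming from dosing and onset dates already collected. The downside is that censoring at the end of treatment may be informative, since subjects stop for progression or toxicity. That is the reason to show both measures and not rely on either alone.

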4.10.3 Pain Medications and Infusion Related Reaction Medications

Pain medications and other treatments administered to prevent or alleviate pain and infusion reactions (including drugs initiated during the infusion period) will be summarized separately for each treatment group. The number and percentage of subjects in each treatment group will be summarized by ATC code. All concomitant medications, including name of drug, indication, dose, frequency, mode of administration, and start/stop day relative to start of study treatment, will be listed by subject.

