Pain was reported in 8 of the 12 subjects and in 15 of 38 (39%) treatment cycles. Mild pain (Grade 1) was most often reported: Grade 1 (82.7% of pain reports), Grade 2 (3.4%) and Grade 3 (13.8%). The median duration of pain was <1 day (IQR: <1 day, <1 day) with most cases resolving within hours of completing the infusion. Opioid analgesics were administered either as premedication or as treatment for pain in 4 subjects and in a minority of treatment cycles (21% of cycles). Pain was commonly managed through conservative measures consisting of decreasing the dinutuximab infusion rate, briefly interrupting the infusion (<30 minutes) and/or administering non-steroidal anti-inflammatory drugs (NSAIDs). Reports of pain in the neck, lower and upper extremities, abdomen, back and pelvis/hip were documented in the EDC. Three subjects reported chest pain and/or pressure during the dinutuximab infusion in cycles 1, 2, 4 and 5. The chest pain/pressure was determined to be non-cardiac in etiology. Pain did not result in any treatment discontinuations and has not required long-term management.

Nine subjects experienced diarrhea. According to the Investigators' assessments, seven events of diarrhea were possibly or probably related to irinotecan, two events were possibly or probably related to irinotecan and dinutuximab, two events were not related to either drug and one event had no causality noted. Diarrhea events lasted a median of 4 days (IQR: 1.5 days, 7 days). Overall, 91.7% of diarrhea reported was graded a CTCAE Grade 1 and 8.3% was graded a CTCAE Grade 2.

The data reviewed at the time of the data cutoff did not demonstrate any safety signals or otherwise trends based upon dosing, infusion rates or number of cycles. Dose levels of 16 mg/m² were tolerated and no unanticipated AEs were reported. No suspected unexpected serious adverse reactions were reported. The SRC concluded that Part 2 of the study should open at a starting dose of dinutuximab of 14 mg/m² and no safety modifications to the protocol were required for Part 2.

The SRC reviewed additional data via a subsequent ad hoc meeting; at that time, 8 of the 12 subjects in Part 1 had received a dose of 16 mg/m²/day or higher. The data at higher doses showed comparable safety and tolerability to the data at lower doses (data on file), and thus the SRC recommended increasing the starting dose of dinutuximab for Part 2 to 16 mg/m²/day.

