6. STUDY TREATMENT

6.1. Dinutuximab Pretreatment (Part 1 and Group B of Part 2)

Dinutuximab will be given on Day 1 (+/- 2 days) of each 21-day cycle. Dinutuximab for injection will be provided by United Therapeutics free of charge for subjects enrolled in Part 1 and randomized to Group B in Part 2 of the study. Ordering information will be provided within the pharmacy manual that will be provided at the start of the study.

Prior to each dinutuximab dose, subjects must receive IV hydration in addition to premedication with antihistamines and antipyretics. From Cycle 2 onwards, premedication with opioid analgesics (morphine or morphine equivalent) may be considered, if in the judgment of the investigator pain is experienced in a prior cycle necessitating use of such medications, as allowed per institutional guidelines. For subjects on opioid medications for pre-existing pain, Medical History should be indicated as the reason for concomitant medication use on the electronic case report form (eCRF). If an opioid is also given as a premedication for possible dinutuximab-

related pain, an additional use should be indicated on the concomitant medication page and premedication should be selected as the category (i.e., two entries with distinct indications).

Subjects must be monitored closely for signs and symptoms of infusion reactions during and following the completion of each dinutuximab infusion in a setting where appropriate medical resources for the treatment of severe infusion reactions are available.

Subjects in Part 1 will be monitored for 4 hours after completion of each dinutuximab infusion. Subjects enrolled in Part 2 Group B will be monitored for 4 hours after completion of each infusion for the first 2 cycles, after which the observation time may decrease to 1 hour or duration deemed clinically necessary by the Investigator (if greater than 1 hour). After each dose increase, subjects should be carefully monitored for tumor lysis syndrome, according to the clinical judgment of the Investigator.

Intravenous Hydration

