- Administer appropriate IV fluids of at least 1 liter one hour prior to initiating each dinutuximab infusion. A volume of less than 1 liter may be administered in subjects at risk for fluid overload, per Investigator discretion. IV hydration may be started during the irinotecan infusion beginning at Cycle 2 when the wait period of 1 hour between the end of the irinotecan infusion and the start of the dinutuximab infusion is no longer required.

Antihistamines and Antipyretics

- Administer an antihistamine such as diphenhydramine (suggested starting dose 50 mg) prior to initiation of dinutuximab and as needed and tolerated during the dinutuximab infusion. Investigators may use their judgment in determining the route (e.g., oral, IV) and dose of antihistamines. If antihistamines are given before the irinotecan infusion, the dose may be halved when antihistamines are given again before the dinutuximab infusion (e.g., 25 mg of diphenhydramine before irinotecan and 25 mg before dinutuximab infusions).
- Administer acetaminophen (suggested starting dose 1,000 mg) approximately 20 minutes prior to each dinutuximab infusion and every 4 to 6 hours as needed for fever or pain. Administer ibuprofen (600-800 mg per dose, not to exceed 3,200 mg in 24 hours) or other NSAID as needed for control of persistent fever or pain.

Opioid Analgesics

- If pain is experienced in a prior cycle necessitating the use of opioid analgesics, subjects may be given opioid analgesics (morphine sulfate or morphine equivalent such as hydrocodone, hydromorphone, oxycodone) as premedication, as allowed per institutional guidelines. Investigators may use their judgment in determining the route (e.g., oral, subcutaneous) and dose of opioid medications. In determining the dose, consideration should be given to whether the subject is currently receiving opioids for pre-existing pain or is opioid naïve.

Other

- For premedications due to *prior* hypersensitivity reaction to dinutuximab, see [Section 6.7.3](#).

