6.7.2. Pain

In general, pain should be managed initially through conservative measures (brief interruption in infusion, decrease in the infusion rate and/or use of NSAIDs or other non-opioid pain medications). Opioid analgesics may also be given. Dose reductions should be undertaken in subsequent cycles (as required - see below), after these measures have been implemented.

| Pain Severity (NCI CTCAE v4.03) | | Dinutuximab Treatment Modification |
|--|---|--|
| Grade 1 | Mild pain | Interrupt infusion for a maximum of 30 minutes, or decrease the infusion rate, and/or administer NSAIDs or other non-opiate pain medication, as needed. The dose of dinutuximab should be increased in subsequent cycle(s) per Table 5 . |
| Grade 2 | Moderate pain; limiting instrumental activities of daily living (ADL) | 
Interrupt infusion for a maximum of 30 minutes, or decrease the infusion rate, and/or administer NSAIDs or other non-opiate pain medication.
 
Administer opioid analgesics (morphine sulfate or morphine equivalent such as hydrocodone, hydromorphone, oxycodone). Consider use of medications used to treat neuropathic pain (e.g., gabapentin, pregabalin, duloxetine, venlafaxine).
 
If Grade 2 pain is adequately managed, the dose of dinutuximab should be increased in subsequent cycle(s) per Table 5.
 
If Grade 2 pain is not adequately managed, the dose should be maintained in the next cycle and opioid analgesics should be given as premedication as allowed per institutional guidelines.
 
If Grade 2 pain is not adequately managed in the next cycle despite maintaining the dose, opioid premedication and/or the measures noted above, the dose should be decreased by 1 dose level in subsequent cycle(s) per Table 5.
 |
| Grade 3 | Severe pain; limiting self care ADL | 
Interrupt infusion for a maximum of 30 minutes, or decrease the infusion rate, and/or administer NSAIDs or other non-opiate pain medication.
 
Administer opioid analgesics (morphine sulfate or morphine equivalent such as hydrocodone, hydromorphone, oxycodone). Consider use of medications used to treat neuropathic pain (e.g., gabapentin, pregabalin, duloxetine, venlafaxine).
 
If Grade 3 pain is adequately managed, the dose of dinutuximab should be increased in subsequent cycle(s) per Table 5.
 
If Grade 3 pain is not adequately managed, the dose should be maintained in the next cycle and opioid analgesics should be
 |

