4.7.2 Concomitant Treatments

Concomitant medications will be coded using the World Health Organization (WHO) Drug Dictionary, version September 2016 (or higher).

The number and percentage of subjects taking concomitant medications during the treatment period will be summarized by anatomical therapeutic chemical (ATC) and preferred term (PT). Although a subject may have taken the same medication multiple times, the subject is counted only once within an ATC classification. The same subject may contribute to two or more preferred terms in the same ATC classification.

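### SAP 4.10.3 mixes mandatory premedication with treatment use, so any Group B antihistamine or antipyretic row will be about 100% by rule and cannot show how many subjects needed these drugs

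*SAP*

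**What the plan says.** SAP 4.10.3 defines one set of drugs, "Pain medications and other treatments administered to prevent or alleviate pain and infusion reactions", including those started during the infusion. It reports subject counts and percentages per treatment group by ATC code and states no split by purpose or timing. Indication and start/stop day appear only in the by-subject listing. For the general concomitant-medication table, SAP 4.7.2 adds that "the subject is counted only once within an ATC classification".

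Protocol 6.1, which covers Part 1 and Group B, says that before each dinutuximab dose "subjects must receive IV hydration in addition to premedication with antihistamines and antipyretics". Table 5 marks both for every cycle. The same drugs may also be given reactively: acetaminophen "approximately 20 minutes prior to each dinutuximab infusion and every 4 to 6 hours as needed for fever or pain", and an antihistamine "prior to initiation of dinutuximab and as needed and tolerated during the dinutuximab infusion". Opioid premedication is optional and starts no earlier than Cycle 2.

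Protocol 10.10.3 describes this summary in two steps. Its first sentence names the same pooled set as the SAP. Its second sentence counts subjects *requiring* analgesics and other drugs for infusion-related reactions. The SAP keeps the first sentence and drops the *requiring* condition from the second. SAP 1 says the SAP takes precedence over the protocol.

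SAP 8.1 lists one dedicated table, 14.3.6.1, whose title covers pain medications only.

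**The concern.** A drug-use table in a safety report is normally read as a measure of how much intervention a regimen needed. Where a drug is compulsory before every dose, that reading fails, because one scheduled dose fills the subject's row and later reactive use changes nothing. Group A has no such premedication rule, so a difference between B and A in these rows mainly reflects the protocol's instruction rather than tolerability.

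Comparing safety between B and A is a secondary objective, and pain and infusion reactions are the expected toxicities of dinutuximab. At stake is whether one descriptive table can answer a simple question for two drug classes: how many subjects were given the drug because something happened to them?

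**Working it through.** The plan states no figure here, so there is nothing to reproduce. The check has four steps.

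**1. Which rows are saturated.**

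| Drug class | Compulsory before dinutuximab? | Also used reactively? | Group B row |
|---|---|---|---|
| Antihistamine | Yes (Protocol 6.1, Table 5) | Yes (6.1; 6.7.3 for Grade 2 reactions) | About 100% by rule |
| Acetaminophen/antipyretic | Yes (6.1, Table 5) | Yes (6.1) | About 100% by rule |
| Opioid | No, optional from Cycle 2 (6.1) | Yes (6.7.2) | Not forced |
| NSAID | No (6.1) | Yes (6.1, 6.7.2) | Not forced |
| Corticosteroid, H2-blocker | No; as premedication only after a Grade 2 reaction (6.7.3) | Steroids yes (6.7.3) | Not forced |

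Within the post-reaction regimen of 6.7.3, only diphenhydramine falls into a row that is already full.

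**2. Sensitivity of a saturated row.** Let c be the share of Group B with at least one recorded premedication dose. The row counts subjects with premedication or treatment use, so:

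- minimum = c, when there is no reactive use or it occurs only in premedicated subjects;
- maximum = 100%;
- width = 100 − c.

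The *must receive* rule implies c = 100%. To allow for missed or unrecorded doses, I also assume 98% and 95%.

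| c | Row can lie between | Width | Minimum count of 184 planned |
|---|---|---|---|
| 100% (rule) | 100% and 100% | 0 points | 184 |
| 98% (assumed) | 98% and 100% | 2 points | 0.98 × 184 = 180.3 |
| 95% (assumed) | 95% and 100% | 5 points | 0.95 × 184 = 174.8 |

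Moving true reactive use from none to everyone shifts the row by at most these widths.

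**3. Part 1 illustration, subject level.** The premedication rule was the same. Protocol 1.15 reports: "Pain was reported in 8 of the 12 subjects and in 15 of 38 (39%) treatment cycles". Because SAP 4.10.3 counts subjects, only the subject figures apply.

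- Row by rule: 12/12 = 100%.
- Subjects with reported pain: 8/12 = 66.7%.
- Counted in the row with no pain reported: 12 − 8 = 4, and 4/12 = 33.3%.

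Reported pain is a proxy. Section 1.15 does not give reactive acetaminophen or antihistamine use, and fever or a reaction could also prompt either drug.

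**4. What a split would show.** A treatment-use row equals the reactive share r. For assumed r of 10%, 30% or 50%, that is about 18, 55 or 92 of 184 subjects, while the premedication row stays near 184. The documents do not give r.

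**The case against.** The best defence is that total drug use, including the premedication burden that dinutuximab imposes, is a legitimate thing to display. A reader who knows Protocol 6.1 will understand a row near 100%. Need for intervention also appears elsewhere. Adverse events are tabulated by preferred term and maximum grade (SAP 4.10.2). Dose reductions, delays and interruptions are summarized (SAP 4.8.1, Table 14.1.3.2). Infusion-reaction grades in Protocol 6.7.3 come close to encoding need for therapy. Part 1 pain was commonly handled by slowing the infusion, "briefly interrupting the infusion (<30 minutes) and/or administering non-steroidal anti-inflammatory drugs (NSAIDs", none of which falls in a saturated row. The by-subject listing keeps indication, and the SAP allows supplementary analyses.

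Most of this stands and limits the point to reactive acetaminophen and antihistamine use. It does not remove it. Pain grades reflect limits on daily activities, and for Grade 1 pain Protocol 6.7.2 says to "administer NSAIDs or other non-opiate pain medication, as needed", so grade does not reveal drug need. Listings leave the reader to count by hand.

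Several stronger readings are tempting but unsupported:

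- *The SAP introduced the pooling.* It did not. The first sentence of Protocol 10.10.3 already pools the two uses. The SAP dropped only the *requiring* condition, which the protocol leaves undefined. That SAP 3.1 records no changes to planned analyses shows little, because SAP 1 undertakes to flag only substantial differences.
- *The inflation can be sized per cycle.* The summary has no cycle-level row.
- *The spurious difference between B and A can be stated in points.* The documents give no Group A rate, and Protocol 6.1 contemplates antihistamines before irinotecan, which Group A also receives.
- *The safety comparison as a whole is compromised.* The adverse event tables do not depend on this display.

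**Conclusion.** The point holds as a minor defect in a descriptive safety display. Any Group B antihistamine or acetaminophen/antipyretic row produced under SAP 4.10.3 will be about 100% by rule. Neither that row nor its contrast with Group A can show how many subjects needed the drug as treatment. The information remains in the listings, and no inferential result is affected.

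The conclusion rests on four assumptions:

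- The once-per-subject rule written in SAP 4.7.2 also governs 4.10.3, as its subject counts imply.
- Premedication is recorded for nearly all subjects given dinutuximab.
- Opioids and NSAIDs have ATC rows separate from acetaminophen. The SAP does not state the ATC level, and a coarser level would spread the saturation.
- The table mock-ups contain no split. SAP 7.2 refers to them, but they are not among the documents, so a split there cannot be ruled out. It is also unclear where an antihistamine row would appear, given the title of Table 14.3.6.1.

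**What to change.** In SAP 4.10.3 and the shell for Table 14.3.6.1:

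1. Tabulate scheduled premedication separately from medication given to treat pain or an infusion reaction, using concomitant-medication category, indication and timing.
2. Report the treatment-use count as the *requiring* count of Protocol 10.10.3, and define that word as drug given to treat an event.
3. Extend the table to infusion-reaction medications, or add a companion table, so that antihistamines have a stated place.
4. Footnote any row where the records cannot separate the two uses as saturated by mandatory premedication.
5. Add a count of subjects with a pain or infusion-reaction event for which treatment was recorded only if the per-event treatment item in Protocol 8.3 is a coded eCRF field. The documents do not say whether it is.

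The cost is SAP and shell wording, one extended or extra table, and modest programming. The main uncertainty is data entry. Protocol 6.1 describes the premedication category and the two-entry rule only for opioids, so the split for antihistamines and acetaminophen depends on how sites recorded category or indication. The footnote covers the case where they did not.
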